## Heterogeneity of Treatment Effects (HTE)

The goal of the HTE analysis is to identify differential treatment effects among subgroups of patients including the following pre-specified factors:

- Physician factors included (1) hospital network, (2) gender, (3) age, (4) years in practice and (5) prior experience with SDM training.
- Patient factors included (1) sex (2) age (3) prior screening history, and (4) overall health.

We will use linear or logistic regression models with the GEE approach to test interactions between study arms and these factors. With the unexpected disruption due to COVID, we added time period (enrollment pre and post COVID) to the HTE analyses post hoc. Due to the exploratory nature of the HTE analysis, we reported treatment effects in each subpopulation when the significance level for the interactions between intervention and these factors was  $\leq 0.1$ .

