*Sample Size*: The study was powered to detect a small to medium effect size difference in the primary outcome, SDM process score. With 500 surveys (250 per arm), assuming an intraclass correlation coefficient of 0.03, the effective patient sample size was estimated at 394, which would enable detection of a difference of 0.28 standard deviations with 80% power and a two-sided significance level of 0.05.

*Statistical methods*: Responders and non-responders were compared to examine potential non-response bias using two-sample t-tests or chi-square tests. Patient sample characteristics were compared between arms using two-sample t-tests or chi-square tests. Multivariable regression models were used to adjust for potential effects of any unbalanced variables.

The following hypotheses were evaluated using an intention to treat approach, and patient outcomes were analyzed based on their physicians' assigned arm regardless of whether the physician completed the training, received the reminder, or discussed CRC screening.

 Examine the effects of the interventions on patients' SDM Process scores and knowledge score:

- a. Compared to the Comparator group, patients seen by physicians in the Intervention arm would report higher SDM Process scores (primary outcome) : We will examine the distribution of the SDM Process score and apply variable transformation techniques if necessary. We will use linear regression models with the Generalized Estimating Equations (GEE) techniques to account for the patients within clinician data structure. We will be able to difference of 0.28 SD for the SDM Process score with 80% power. Studies using the SDM Process survey have found effect sizes ranging from 0.39SD – 0.88SD when comparing sites that used have formal decision support (coaching or decision aids) and those that did not. Although we have sufficient power to detect a smaller difference, we are interested in a meaningful difference 0.4SD or higher.

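### Reporting subgroup effects on condition that the interaction reaches p ≤ 0.1, across ten factors, selects results on significance and overstates the contrasts that pass

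*SAP*

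**What the plan says.** The SAP section Heterogeneity of Treatment Effects (HTE) lists nine pre-specified factors. Five belong to the physician: "Physician factors included (1) hospital network, (2) gender, (3) age, (4) years in practice and (5) prior experience with SDM training". Four belong to the patient: "Patient factors included (1) sex (2) age (3) prior screening history, and (4) overall health". A tenth came later: "we added time period (enrollment pre and post COVID) to the HTE analyses post hoc".

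The method is an interaction test for each factor: "We will use linear or logistic regression models with the GEE approach to test interactions between study arms and these factors". The reporting rule follows: "we reported treatment effects in each subpopulation when the significance level for the interactions between intervention and these factors was" at or below 0.1. The reason given is "Due to the exploratory nature of the HTE analysis".

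The section does not name the outcomes to be analysed, does not say how age, years in practice or overall health will be categorised, and states no multiplicity adjustment or shrinkage. It does not say that interaction estimates or subgroup effects for the other factors will be shown. The protocol describes no HTE analysis.

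**The concern.** A p-value threshold used as a condition for reporting acts as a filter. Ten factors enter, and the subgroup effects that come out are those whose interaction estimate happened to be large relative to its standard error. This has three consequences.

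- Some factors will pass by chance, and the SAP gives the reader no expected number.
- The interaction contrast for a factor that passes is too large on average, whether or not a real interaction lies behind it.
- A factor that does not pass leaves no estimate, so a precise finding of little difference looks the same as an imprecise one.

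The third consequence matters most for COVID period. Under the protocol's Recruitment Procedures, patients first received a study letter about two weeks before the visit and a call one to three days before it. In the COVID-19 version most visits moved to telehealth and study material arrived only after the visit. Visit mode and pre-visit contact therefore changed together, and readers will want the effect by period whatever its p-value.

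**Working it through.** **Inputs.** From the SAP, Sample Size: 500 surveys (250 per arm), intraclass correlation 0.03, effective sample size 394, detectable difference 0.28 SD at 80% power and two-sided 0.05. From the protocol, Research Design and Methods: about 10 patients per clinician. From the SAP, HTE: ten factors, threshold 0.1. Assumed here: two-level factors with an even split, and independent tests.

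**The plan's own figure.** Design effect = 1 + (10 − 1) × 0.03 = 1.27, and 500 / 1.27 = 393.7, which matches 394. Detectable difference = (1.960 + 0.842) × √(2/197) = 0.282 SD, which matches 0.28. The SAP gives no power or error rate for the HTE analysis.

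**Chance flags per outcome if no interaction is real.**
- Expected number: 10 × 0.1 = 1.0 (0.9 for the nine pre-specified factors).
- At least one: 1 − 0.9¹⁰ = 65.1% (1 − 0.9⁹ = 61.3% for nine).
- Two or more: 26.4%.

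Correlation between factors lowers the 65% but leaves the expected count at 1.0.

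**Standard error of an interaction contrast, in SD units.**
- Physician factor: 4 × √(1.27/500) = 0.202.
- Patient factor balanced within clinicians, where the clinician component cancels and leaves 1 − 0.03 = 0.97: 4 × √(0.97/500) = 0.176.

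**Smallest contrast that passes.** 1.645 × 0.202 = 0.33 SD; 1.645 × 0.176 = 0.29 SD.

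**Mean absolute size of a null contrast that passes.** SE × φ(1.645)/0.05 = SE × 2.063, giving 0.42 SD (physician factor) and 0.36 SD (patient factor).

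**Chance that a real interaction misses the gate.** Power = Φ(δ/SE − 1.645) + Φ(−δ/SE − 1.645).

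| True interaction | Physician factor: power / missed | Patient factor: power / missed |
|---|---|---|
| 0.28 SD | 40% / 60% | 48% / 52% |
| 0.40 SD | 63% / 37% | 73% / 27% |

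**Overstatement of a real interaction that passes.** By simulation with effective N = 394 and an even split, the average overstatement is 1.7 times for a true 0.28 SD and 1.3 times for a true 0.40 SD. With N = 500 the factors are 1.5 and 1.2.

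**COVID period.** The SAP's enrolment dates (October 2019 to 12 March 2020, then 25 May 2020 to April 2021) give roughly a one-third to two-thirds split if accrual was uniform. SE = √(4 × 0.97/500 × (3 + 1.5)) = 0.187 SD. Power for a true 0.28 SD difference is about 44%, so it would miss the gate about 56% of the time.

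**Share of flagged factors that are chance findings.** With t real interactions among ten, expected false flags are (10 − t) × 0.1 and expected true flags are t × power. Using the physician-factor power:

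| Real interactions | Share false at 0.28 SD | Share false at 0.40 SD |
|---|---|---|
| 0 | 100% | 100% |
| 1 | 69% | 59% |
| 2 | 50% | 39% |
| 3 | 37% | 27% |

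The shares are equal at t = 1/(power + 0.1): 2.0 factors at 0.28 SD and 1.4 at 0.40 SD.

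**The case against.** The SAP does several things well. It lists its factors, uses interaction tests rather than separate p-values within subgroups, states the threshold, calls the analysis exploratory and labels the period factor post hoc. A threshold of 0.1 also gives more power than 0.05 would. An informed reader can work out the one-in-ten chance rate. All of this stands and limits the harm. It does not remove the selection: exploratory status is a reason to show every estimate with its uncertainty.

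The rule does not contain the word only, and the SAP does not say that the other interaction estimates will be withheld. That is correct. Still, a stated condition for reporting has no other natural purpose, and nothing commits the authors to showing the rest.

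Four stronger readings are tempting, and the documents do not support them.

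- *Most reported subgroup findings will be chance.* This holds only if fewer than about two of the ten interactions are real at 0.28 SD, or about 1.4 at 0.40 SD. The documents give no basis for that number.
- *Every reported subgroup effect is pushed away from zero.* Selection acts on the contrast. With an even split, a chance contrast of 0.42 SD moves one subgroup up and the other down by about 0.21 SD, and one of them may move towards zero.
- *A chance flag would meet the SAP's own standard of importance.* The statement "we are interested in a meaningful difference 0.4SD or higher" concerns the difference between arms in the primary score, not a difference between two such differences.
- *Moderate heterogeneity is more often hidden than shown.* This is so at 0.28 SD under the even-split assumption, but not at 0.40 SD.

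The even binary split is also only an approximation. Hospital network has five levels and needs a joint test, and physician age and years in practice are probably correlated.

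**Conclusion.** The concern holds as a reporting defect of moderate weight. Followed as written, the rule selects subgroup results on significance. If no interaction is real, about one chance flag per outcome is expected, with a 65% probability of at least one under independence and somewhat less under correlation. Contrasts that pass are overstated: a null one averages 0.36 to 0.42 SD, and a true 0.28 SD one is inflated about 1.5 to 1.7 times. Real interactions of 0.28 SD miss the gate 52% to 60% of the time, and those of 0.40 SD 27% to 37%.

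The sizes rest on the SAP's planned sample and intraclass correlation, together with the assumed even two-level factors; an uneven split would give larger standard errors. The finding of selection rests on none of these assumptions. Whether flagged factors are mainly chance findings cannot be settled from the documents. The primary and secondary comparisons between arms are untouched.

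**What to change.** Drop p ≤ 0.1 as a condition for reporting. For every outcome given an HTE analysis, name the outcome and report the interaction estimate, its 95% CI and p-value, and the effect at each level, for all nine pre-specified factors and the period factor, in one table or forest plot. Keep the period factor's existing post hoc label. State that there is no multiplicity adjustment and that about one in ten null interactions reaches p ≤ 0.1 by chance.

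The cost is a change of SAP wording and one supplementary exhibit. The interaction models are already planned, and the SAP's past tense does not prevent a complete supplement. The downside is a longer supplement.
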